5.2.3.3. Critical care resource use post-arrest (objective 3c)

Outcome defined as number of days in a critical care unit (obtained through data linkage with the CMP).

Patients included in the model will be all adult patients (aged 16 years or over) meeting the inclusion for objectives 3a and 3b who survive the initial arrest (ROSC greater than 20 minutes).

As the important risk factors and their relationships with the outcome may be very different from those considered previously, the new risk models for critical care and hospital resource use will be developed, de novo, using the same methods as previously applied to develop the original risk models for ROSC greater than 20 minutes and survival to hospital discharge.

5.2.3.4. Subsequent hospital resource use and costs (objective 3d)

Outcome defined as number of days in acute hospital, either during the original hospital episode (as identified from NCAA data) or subsequent hospital episodes (as identified through data linkage with HES).

Patients included in the model will be all adult patients (aged 16 years or over) meeting the inclusion for objectives 3a and 3b who survive the initial arrest (ROSC greater than 20 minutes).

6. Ethical compliance

6.1. Approval by ethics committee

The Medical Research Council/Health Research Agency (HRA) online decision tool (http://hra-decisiontools.org.uk/ethics/) indicates that approval by an NHS Research Ethics Committee is not required for secondary research using existing pseudonymised data, provided the research team could not identify the participants either directly from the data or from its combination with other information likely to come into their possession. As members of the research team have access to patient identifiable data for the CMP and NCAA, it is not clear that this final condition can be met. An application will therefore be made to an NHS Research Ethics Committee for approval of the study.

6.2. Confidentiality and data protection

The ICNARC CTU will act to preserve participant confidentiality and will not disclose or reproduce any information by which participants could be identified. ICNARC is registered under the Data Protection Act 1998 and all ICNARC CTU staff undergo data protection and ICH GCP training.

All five national clinical audits involved in this study operate under Section 251 of the NHS Act 2006, permitting the use of patient identifiable data without consent for specified purposes. A further application will be made to the HRA Confidentiality Advisory Group to request approval under Section 251 for the creation of the linked pseudonymised dataset for this Study.

Prior to data linkage, all necessary approvals will be obtained from the Data Controllers of each data source, including from the Healthcare Quality Improvement Partnership (HQIP) for the two HQIP-funded national clinical audits (National Diabetes Audit and National Adult Cardiac Surgery Audit).

As the study uses existing data and does not involve any change to usual care for patients, an independent Data Monitoring Committee (DMC) will not be required.

7. Study closure

7.1. End of study

The "end of the study" will be when all analyses are complete and the Final Report of the Study is submitted to the funder, at which point the declaration of end of study form will be submitted to the REC by the ICNARC CTU.

7.2. Archiving study data

At the end of the Study, the ICNARC CTU will archive securely all centrally-held study-related documents and electronic data for a minimum of ten years in accordance with the ICNARC CTU Standard Operating Procedure (SOP) on archiving trial/study data based on ICH GCP guidelines. After 10 years, arrangements for confidential destruction of all documents and data will then be made.

8. Study management

8.1. Good research practice

The study will be managed according to the MRC's Guidelines for Good Clinical Practice in Clinical Trials and Good Research Practice: Principles and guidelines, which are based on the principles of ICH GCP. The ICNARC CTU has developed its own policies and procedures, based on these MRC guidelines, for the conduct of all its research activities. In addition, ICNARC has contractual confidentiality agreements with all members of staff. Policies regarding alleged scientific misconduct and breach of confidentiality are reinforced by disciplinary procedures.

8.2. Study Management Group

The day-to-day running of the Study will be overseen by a Study Management Group (SMG) consisting of the Chief Investigator, the ICNARC co-investigators, [name] (National Audit Data Manager, ICNARC) and a Research Administrator. The SMG will meet at least monthly to review progress.

8.3. Study Steering Committee

The Chief Investigator will report to the Study Steering Committee (SSC), which will monitor progress of the Study against timelines and milestones. The SSC will be chaired by an independent member, [name], Director of the Clinical Effectiveness Unit, Royal College of Surgeons and Senior Lecturer in Health Services Research, London School of Hygiene and Tropical Medicine.

8.4. Clinical Advisory Groups

For each specific clinical focus of the study, a Clinical Advisory Group will meet regularly (using a combination of face-to-face meetings and teleconference), led by the relevant clinical coinvestigators, to provide clinical advice and guidance.

9. Sponsorship and Indemnity

ICNARC is the Sponsor for the Study and holds professional indemnity insurance (Markel International Insurance Co Ltd) to meet the potential legal liability of the Sponsor and employees for harm to participants arising from the design and management of the research.

10. Funding

The Study is funded by the NIHR Health Services & Delivery Research (HS&DR) Programme (Project No. 14/19/06).

11. Dissemination

The results of the Study will be widely and actively disseminated.

Results will be presented at the Annual Meeting of the Case Mix Programme and the Annual Meeting of the National Cardiac Arrest Audit and at relevant scientific and health services conferences and meetings.

A Final Report to the HS&DR programme will present a detailed description of the Study and the results along with implications for policy and practice and recommendations for future research. Articles will be prepared for publication in academic peer-reviewed journals and relevant professional journals.

In line with NIHR guidance on maximising the use of data from publicly funded research, the final anonymised, linked dataset will be made available on request for further epidemiological and methodological research.

References

- 1. Department of Health. High Quality Care For All--NHS Next Stage Review Final Report. The Stationary Office, 2008.
- 2. N., B., *Time for a new approach to assessing the quality of hospitals in England.* . BMJ, 2013. **347**: p. f4421.
- 3. N., B., *Assessing the quality of hospitals.* . BMJ, 2010. **340**: p. c2066.
- 4. Harrison DA, P.G., Carpenter JR et al., *A new risk prediction model for critical care:* the Intensive Care National Audit & Research Centre (ICNARC) model. Crit Care Med, 2007. **35**: p. 1091-8.
- 5. Harrison DA, L.N., Haddow C et al., *External validation of the Intensive Care National Audit & Research Centre (ICNARC) risk prediction model in critical care units in Scotland.* BMC Anesthesiol, 2014. **14**: p. 116.

Appendix 1 Fields to be included in final pseudonymised data extracts

Case Mix Programme
Common key
Unique hospital identifier (anonymous)
Unique critical care unit identifier (anonymous)
Deprivation quintile
Residence prior to admission to acute hospital
Age (whole years)
Ethnicity
Body mass index
Sex
Date of admission to hospital
Date of admission to the critical care unit
Time of admission to the critical care unit
Cardiopulmonary resuscitation within 24 hours prior to admission to the critical care unit
Location (in)
Classification of surgery
Hospital housing transient location (in)
Prior location (in)
Hospital housing non-transient location (in)
Date of original admission to/attendance at acute hospital
Date of original admission to ICU/HDU
Admission type
Primary reason for admission to the critical care unit
Secondary reason for admission to the critical care unit
Evidence available to assess past medical history
Severe conditions in the past medical history – respiratory
Severe conditions in the past medical history – cardiovascular
Severe conditions in the past medical history – renal
Severe conditions in the past medical history – liver
Severe conditions in the past medical history – metastatic disease
Severe conditions in the past medical history – haematological malignancy
Severe conditions in the past medical history – immunocompromise
Dependency prior to admission to acute hospital
Evidence available to abstract physiology data
Lowest central temperature
Highest central temperature
Lowest non-central temperature
Highest non-central temperature
Lowest systolic blood pressure
Paired diastolic blood pressure (for lowest systolic blood pressure)

Highest systolic blood pressure

Paired diastolic blood pressure (for highest systolic blood pressure)

Lowest heart rate

Highest heart rate

Lowest non-ventilated respiratory rate

Highest non-ventilated respiratory rate

Lowest ventilated respiratory rate

Highest ventilated respiratory rate

Lowest PaO₂

Associate FiO₂ (from arterial blood gas with lowest PaO₂)

Associate PaCO₂ (from arterial blood gas with lowest PaO₂)

Associate pH (from arterial blood gas with lowest PaO₂)

Lowest pH

Associate PaCO₂ (from arterial blood gas with lowest pH)

Lowest serum bicarbonate

Highest serum bicarbonate

Lowest serum sodium

Highest serum sodium

Lowest serum potassium

Highest serum potassium

Lowest serum glucose

Highest serum glucose

Highest blood lactate

Highest serum urea

Lowest serum creatinine

Highest serum creatinine

Total urine output

Lowest haemoglobin

Highest haemoglobin

Lowest platelet count

Highest platelet count

Lowest white blood cell count

Associated neutrophil count (for lowest white blood cell count)

Highest white blood cell count

Associated neutrophil count (for highest white blood cell count)

Pupil reactivity (left eye)

Pupil reactivity (right eye)

Sedated or paralysed and sedated for whole of first 24 hours in the critical care unit

Neurological status

Lowest total Glasgow Coma Score (GCS)

Associated eye component (for lowest total GCS)

Associated motor component (for lowest total GCS)

Associated verbal component (for lowest total GCS)

Associated intubation status (for lowest total GCS)

Highest level of care received in the first 24 hours in the critical care unit

Number of basic respiratory support days

Number of advanced respiratory support days

Number of basic cardiovascular support days

Number of advanced cardiovascular support days

Number of renal support days

Number of neurological support days

Number of gastrointestinal support days

Number of dermatological support days

Number of liver support days

Number of Level 3 days

Number of Level 2 days

Number of Level 1 days

Number of Level 0 days

Treatment withheld/withdrawn

Status at discharge from the critical care unit

Date when fully ready to discharge

Time when fully ready to discharge

Reason for discharge from the critical care unit

Timeliness of discharge from the critical care unit

Date of discharge from the critical care unit

Time of discharge from the critical care unit

Level of care received at discharge from the critical care unit

Expected dependency post-acute hospital discharge

Brainstem death declared

Date of declaration of brainstem death

Time of declaration of brainstem death

Date of death

Time of death

Location (out)

Hospital housing location (out)

Date of ultimate discharge from ICU/HDU

Status at ultimate discharge from ICU/HDU

Date of discharge from hospital

Status at discharge from hospital

Destination post-discharge from hospital

Date of ultimate discharge from acute hospital

Status at ultimate discharge from acute hospital

Residence post-discharge from acute hospital

National Cardiac Arrest Audit

Common key

Unique hospital identifier (anonymous)

Age (whole years)

Sex

Ethnicity

Date of admission to/attendance at/visit to hospital

Reason for admission to/attendance at/visit to hospital

Date/time of 2222 call

Status at team arrival

Location of arrest

Presenting/first documented rhythm

Date/time resuscitation started

Date/time resuscitation stopped

Reason resuscitation stopped at end of team visit

Transient post-arrest location

Post-arrest location

Status at discharge from hospital

Sedated at discharge from hospital

CPC at discharge from hospital

Method used to assess CPC at discharge from hospital

Date of discharge from hospital

Date/time of death

UK Renal Registry

Common key

ERF patient flag

Date first seen by Renal Physician

Serum creatinine when first seen

Date of renal referral

Date of 1st eGFR of CKD5 (Date of Start of CKD5)

1st eGFR at start of CKD5

Date of 2nd eGFR 90 days later (CKD5)

2nd eGFR 90 days later (CKD5)

Date 1st ERF treatment

Primary disease code (ICD)

EDTA primary renal disease code

Date of last creatinine prior to start of ERF

Last creatinine prior to start of ERF

National Diabetes Audit

Common key

Diabetes Diagnosis Date

Diabetes Diagnosis Type Code

HbA1c (value and date)

National Adult	Cardiac	Surgery	Audit
----------------	---------	---------	-------

Common key

Angina status pre-surgery

Dyspnoea status pre-surgery

Number of previous MIs

Interval between surgery and last MI

Previous PCI

Previous cardiac surgery

Diabetes management

Cigarette smoking history

History of hypertension

Actual creatinine at time of surgery

Renal function/Dialysis

History of pulmonary disease

History of neurological disease

History of neurological dysfunction

Extracardiac arteriopathy

Pre-operative heart rhythm

Ejection fraction category

PA systolic

Intravenous nitrates or any heparin

Intravenous inotropes prior to anaesthesia

Ventilated (Pre-Operation)

Cardiogenic shock (Pre-Operation)

Date and time of operation

Operative urgency

Number of previous heart operations

CABG

Valve

Major aortic

Other Cardiac Procedures

Other Actual Cardiac Procedures

Total number of distal coronary anastomoses

Number of valves replaced/repaired

Native aortic valve pathology

Reason for repeat aortic valve operation

Aortic valve procedure

Native mitral valve pathology

Reason for repeat mitral valve operation

Mitral valve procedure

Native tricuspid valve pathology

Reason for repeat tricuspid valve operation

Tricuspid valve procedure

Native pulmonary valve pathology

Reason for repeat pulmonary valve operation

Pulmonary valve procedure

Number of aorta segments operated on

Aortic pathology – Root Segment Code 1

Aortic pathology – Ascending Segment Code 2

Aortic pathology – Arch Segment Code 3

Aortic pathology - Descending Aorta Segment Code 4

Aortic pathology – Abdominal Segment Code 5

Cardiopulmonary bypass

Intra-aortic balloon pump used (pre-operative)

Impeller device used (pre-operative)

Ventricular assist device used (pre-operative)

Other Support device used (pre-operative)

Intra-aortic balloon pump used (intra-operative)

Impeller device used (intra-operative)

Ventricular assist device used (intra-operative)

Other Support device used (intra-operative)

Intra-aortic balloon pump used (post-operative)

Impeller device used (post-operative)

Ventricular assist device used (post-operative)

Other Support device used (post-operative)

Cumulative bypass time

Cumulative cross clamp time

Total circulatory arrest time

Additive Euroscore

Logistic Euroscore

Hospital Episode Statistics – Admitted Patient Care data

Common key

Date of admission

Method of admission

Source of admission

Date of discharge

Destination on discharge

Method of discharge

Beginning of spell

Date episode ended
Date episode started
Duration of spell
End of spell
Episode duration
Episode order
Episode status
Episode type
All diagnosis codes
Primary diagnosis (4 characters)
All operative procedure codes
Main operative procedure code 3 character
Date of operations
Patient classification
Dominant procedure
Healthcare resource group: version 3.5
NHS-generated HRG code
NHS-generated HRG code version number
SUS generated core spell HRG
SUS generated HRG
SUS generated HRG version number
SUS generated spell ID
Code of GP practice
Record Identifier

HES-linked O	NS Morta	lity data
--------------	----------	-----------

Fact of Death

Date of Death

ICD 10th Revision Coded Cause(s) of Death

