1.3. In-hospital cardiac arrest

Until recently, no validated risk models existed for predicting outcomes following in-hospital cardiac arrest. The National Cardiac Arrest Audit (NCAA), the national clinical audit of in-hospital cardiac arrest coordinated by ICNARC in collaboration with the Resuscitation Council (UK), was therefore established with a dataset including established important risk factors for outcomes following in-hospital cardiac arrest with a view to subsequent development of a risk model. In the previous research study, we developed and validated two novel risk models for in-hospital cardiac arrest. Based on over 14,000 in-hospital cardiac arrests in 122 hospitals, risk models were developed to predict both return of spontaneous circulation (ROSC) greater than 20 minutes and survival to hospital discharge. These models demonstrate good discrimination (c index 0.72 and 0.81, respectively) in external validation data and have enabled risk-adjusted comparisons among hospitals to be included, for the first time, in routine reporting for NCAA.

Simultaneous to our work developing risk models for NCAA, a risk model for predicting hospital mortality following in-hospital cardiac arrest was published from the United States Get With the Guidelines—Resuscitation registry. This identified largely similar risk factors to the NCAA risk models, but included additional predictors not available in the NCAA dataset, most notably preexisting comorbidities. Data linkage with HES will enable calculation of comorbidity indices from diagnoses and procedural codes recorded during the hospital episode, an approach that has recently been applied successfully in the UK Renal Registry. Combining this information with the existing risk factors will enable us to determine the contribution of chronic health conditions to outcome from in-hospital cardiac arrest with a view to either routinely linking data in the future, or establishing which comorbidity fields are important to collect directly within NCAA.

While many patients do not survive the initial resuscitation attempt, the treatment of those that do requires substantial resources and many patients will be admitted to a critical care unit. Data linkage between NCAA and the CMP will allow us to better understand patterns of critical care resource use and organ support following successful resuscitation and develop prediction models for likely resource use.

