5.2.3. Risk models for in-hospital cardiac arrest (objective 3)

5.2.3.1. ROSC greater than 20 minutes and survival to hospital discharge (objective 3a)

Outcomes defined as ROSC greater than 20 minutes and survival to hospital discharge (hospital survival) from the existing NCAA data, the outcomes for the current risk models.

Patients included in the models will be all patients (aged 28 days or over) who received chest compressions and/or defibrillation following an in-hospital cardiac arrest and were attended by the hospital-based resuscitation team.

The starting point for the new risk models will be the previously developed risk models for each outcome.

New risk factors: pre-arrest risk factors obtained by data linkage with HES, the Charlson comorbidity index ^[28] and Elixhauser comorbidity measure ^[29] will be derived from International Classification of Disease (ICD-10) diagnostic codes and Office of Population Censuses and Surveys (OCPS) procedural codes, using methods employed recently by the UK Renal Registry ^[16], will be assessed for the optimal categorisation of the complex categorical risk factors.

5.2.3.2. Survival to 30 days, 90 days and 1 year and time to death (objective 3b)

Outcome defined as mortality at 30-days, 90-days and 1-year and days from cardiac arrest to death using the date of death obtained by data linkage with ONS.

Patients included in the models will be all patients (aged 28 days or over) who received chest compressions and/or defibrillation following an in-hospital cardiac arrest and were attended by the hospital-based resuscitation team.

The starting point for each new risk model will be the risk model for survival to hospital discharge developed in objective 3a.

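### If objective 3a takes comorbidity from the index hospital episode, patients not yet admitted at the arrest have that record only if they survive to admission, so the predictor's availability depends on the outcome

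*Protocol*

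**What the plan says.** Section 5.2.3.1 models two outcomes, ROSC greater than 20 minutes and survival to hospital discharge. The population is "all patients (aged 28 days or over) who received chest compressions and/or defibrillation following an in-hospital cardiac arrest", provided the hospital resuscitation team attended. Being an inpatient at the time is not required. The National Cardiac Arrest Audit (NCAA) field list in Appendix 1 contains "Date of admission to/attendance at/visit to hospital", so the audit data include people who were attending or visiting.

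The new predictors are the Charlson and Elixhauser measures. Appendix 1 lists one HES extract, "Hospital Episode Statistics – Admitted Patient Care data", with "All diagnosis codes" among its fields. No outpatient or emergency-attendance extract is listed.

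The protocol describes which episodes supply the codes in two ways:
- Section 1.3: "Data linkage with HES will enable calculation of comorbidity indices from diagnoses and procedural codes recorded during the hospital episode".
- Section 5.2.3.1: "pre-arrest risk factors obtained by data linkage with HES", with no look-back period given.

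Appendix 2, step 1, will explore missing data and the completeness of linkage and will compare ways of handling missing values. It gives no rule for a record that is absent because the patient died before admission.

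**The concern.** An inpatient has an admitted record of the episode whether or not the arrest is survived. A person who arrests while attending or visiting has one only after surviving long enough to be admitted. Under the section 1.3 wording, the existence of the predictor in this subgroup is therefore tied to ROSC and survival, the outcomes being modelled.

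This is a different problem from diagnoses coded after the arrest entering the index episode. Removing every post-arrest code would still leave the non-admitted deaths without a record.

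Two uses depend on the result. Section 1.3 intends to judge from this analysis whether to link routinely or which comorbidity fields NCAA should collect. Section 5.2.3.2 makes the 3a hospital-survival model the starting point for the longer-term mortality models in 3b.

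**Working it through.** **Inputs from the protocol.** Section 3.2 gives about 56,000 arrests and 10,000 survivors: 10,000/56,000 = 17.9% survival. The protocol states no comorbidity effect and no share of arrests in people not yet admitted, so there is no figure of its own to reproduce.

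**Assumptions, for illustration only.** Share of arrests in people not yet admitted, *f*: 2% to 15%. Share of those who survive to admission, *a*: 30% to 60%. Share of the rest with a usable earlier admitted record, *h*: 0 or 80%. Comorbidity prevalence, *p*: 60% (40% as an alternative). No true effect of comorbidity.

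**Step 1: who has an index record.**

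| Status at arrest | Survives to admission | Dies first |
|---|---|---|
| Inpatient | Yes | Yes |
| Not yet admitted | Yes | No (earlier episodes only, if any) |

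**Step 2: absent record scored as no comorbidity, outcome ROSC.** Let *s* be the share of patients without ROSC who have no record, taken as the non-admitted share when no earlier records are used. Recorded prevalence is *p* with ROSC and (1 − *s*)*p* without.

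OR = [*p*/(1 − *p*)] / [(1 − *s*)*p* / (1 − (1 − *s*)*p*)]

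- *p* = 60%, *s* = 5%: 1.500/(0.57/0.43) = 1.13
- *s* = 10%: 1.500/(0.54/0.46) = 1.28
- *s* = 15%: 1.500/(0.51/0.49) = 1.44
- *p* = 40%, same shares: 1.09, 1.19, 1.29

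If 80% have a usable earlier admission, *s* falls to 1%, 2% and 3%. At *p* = 60% the odds ratios are then 1.03, 1.05 and 1.08.

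**Step 3: patients without a record dropped.** Share without a record = *f*(1 − *a*)(1 − *h*), all taken to have died. Complete-case survival = 17.9%/(1 − that share).

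- *h* = 0: from 0.02 × 0.4 = 0.8% (about 450 arrests) to 0.15 × 0.7 = 10.5% (about 5,900). That is 1.0% to 12.8% of the 46,000 non-survivors, and complete-case survival is 18.0% to 20.0%.
- *h* = 80%: 0.2% to 2.1% (about 90 to 1,200 arrests), and survival is 17.9% to 18.2%.

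In this null scenario prevalence stays at *p* in both outcome groups, so the comorbidity odds ratio stays at 1.00. What moves is the intercept, calibration and any effect of arrest location.

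**Step 4: could the Step 2 artefact enter the model?** Take hospital survival, with a share *m* of arrests unrecorded, all dead and scored as no comorbidity. Recorded patients survive at 17.9%/(1 − *m*). For *m* = 5% and *p* = 60%, those scored as comorbid survive at 18.8%. Those scored as not comorbid survive at 0.38 × 18.8%/(0.38 + 0.05) = 16.6%, so the OR is 1.16. For *m* = 1%, 2% and 10% the OR is 1.03, 1.06 and 1.35.

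Appendix 2, step 3, uses the BIC to judge which predictors matter. The penalty per term is ln(56,000) = 10.9. The unadjusted standard error of the log OR is √(1/6,000 + 1/4,000 + 1/27,600 + 1/18,400) = 0.0225. A single term is favoured once the OR exceeds exp(√10.9 × 0.0225), about 1.08. A false effect at 5% unrecorded would be kept; one at 2% would not.

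**The case against.** The strongest reply is that the model specification itself calls these factors pre-arrest, and that the common key in section 4.1 links all records of one patient. Earlier admissions exist whatever the outcome of the arrest. On that reading the problem largely disappears, as the 80% scenario shows. This stands, and it limits the point to index-episode codes. It does not remove it, because section 1.3 states the index-episode reading and nothing reconciles the two.

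A reader might infer several stronger claims that the protocol does not support:

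- *Attenders and visitors who die have no HES data at all.* Only the index record is missing, and earlier admissions may supply codes. The protocol does not say when an admitted record is created; the index-record point rests on what an admitted-patient dataset is.
- *Comorbidity will look protective.* That needs absent records scored as zero, and no text says so. Dropping the patients leaves the null odds ratio at 1.00.
- *Imputation cannot help.* Outcome is recorded and admission status can be approximated. Imputation is therefore possible if the comorbidity–outcome relation is assumed to be similar in admitted patients. That assumption would need testing.
- *The bias would mask a true harmful odds ratio of 0.8.* Offsetting 0.8 needs a false odds ratio of 1/0.8 = 1.25. At 60% prevalence that takes roughly 10% or more without a record and no use of earlier admissions.

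It is also fair to say that look-back windows and missing-record rules often sit in an analysis plan, which is not at hand, and that section 5.1.4 leaves plans to be finalised before modelling. The point does not rest on that missing detail. It follows from three choices the protocol does state: the population, the HES source and the index-episode wording.

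**Conclusion.** The point holds in a limited form. For arrests in people not yet admitted, an index-episode admitted record depends on surviving to admission. If comorbidity is taken as section 1.3 describes, its availability depends on the 3a outcome.

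The consequence depends on handling. Zero-scoring pushes comorbidity towards looking protective, by an amount between negligible and material across the assumed ranges. Dropping the patients selectively removes deaths. Both sizes depend on a non-admitted share that the protocol does not give and on how many of these patients have usable earlier admissions. Patients who were inpatients at the arrest are unaffected. Because the repair is cheap and the 3a result decides what the audit will collect, it should be settled before modelling.

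**What to change.** Reconcile section 1.3 with section 5.2.3.1, and state in 5.2.3.1:

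1. Charlson and Elixhauser are derived for every patient from admitted episodes that ended before the arrest, over the same fixed look-back whatever the outcome. A patient with no earlier admission is then treated alike whether or not the arrest is survived.
2. If index-episode codes are also used, they are used only for patients who were inpatients at the arrest. Identify these from the NCAA location of arrest and reason for admission, attendance or visit. HES dates alone will not do: they carry no time and cannot order same-day events. An attender resuscitated and admitted that day would look already admitted, while the matching death would drop out.
3. An absent index record is not scored as no comorbidity.
4. The 3a models, and the 3b models built on them, are also reported in inpatients only, as a sensitivity analysis.

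The fields are already in Appendix 1. The HES extract must reach back far enough before 1 April 2011, the start of the objective 3 data, to fill the look-back for the earliest arrests. The cost is that comorbidity first coded in the index episode is lost for non-inpatients, plus a little more analysis.
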